11.4.2.3 Physical examination, vital signs, and electrocardiogram

Potentially clinically significant findings observed during the on-treatment period for vital signs (including but not limited to blood pressure, heart rate, respiratory rate, etc) and ECG (QTc, PR interval, etc) will be summarized by study cohort and treatment group, as well as by dose levels among avalglucosidase alfa-treated patients. Listings of abnormal findings/values from these data as well as from PE assessment inclusive of body weight and height, as well as head circumference and Tanner stage, will be presented.

11.4.2.4 Anti-avalglucosidase alfa and anti-alglucosidase alfa antibodies, neutralizing antibodies, and other immunogenicity testing

Percentage of patients who seroconverted to avalglucosidase alfa, time to seroconversion and peak anti-avalglucosidase alfa antibody titer will be summarized using summary statistics.

Anti-avalglucosidase alfa and anti-alglucosidase alfa antibody titer values will be summarized using summary statistics at each study visit. All data will be presented in listings for each patient.

By patient listings will also display results of neutralizing antibody, circulating immune complex, anti-avalglucosidase alfa IgE antibody, serum tryptase activity, complement activation, and skin testing performed. Descriptive summaries may also be provided as appropriate.

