2 STATISTICAL AND ANALYTICAL PROCEDURES

The interim analysis will be performed when all Cohort 3 patients have completed the 6-month (25 weeks) primary analysis period and will include a formal database lock and analyses of safety (including adverse events, physical examinations and growth, clinical laboratory evaluations, electrocardiogram [ECG], vital signs and immunogenicity), PK, efficacy (including GMFM-88, GMFCS-E&R, Pompe-Pediatric Evaluation of Disability Inventory [PEDI] mobility, Quick Motor Function Test [QMFT], echocardiography [ECHO], Eyelid position measurements including Interpalpebral fissure distance [IPFD], Margin reflex distance-1 [MRD-1], Margin pupil distance [MPD], total creatine kinase [CK], CK with MB fraction, and Composite Score Constructed Considering 3 Domains: GMFM-88 and GMFCS-E&R, Ptosis, and Respiratory Function), PD (urinary Hex4 level), and exploratory effect of avalglucosidase alfa treatment on functional endurance, six-minute walk test (6MWT), respiratory function (including Pulmonary Function Testing [PFT] and ventilator use diary), PedsQL Generic Core Scales, HRQOL, pain (including PedsQL Pediatric Pain Questionnaire and Visual Analogue Scale [VAS]), developmental disability (including Bayley Scale of Infant and Toddler Development, Third Edition [Bayley-III] and Leiter International Performance Scale, Third Edition [Leiter-3]), and hearing testing in patients with IOPD. A Clinical study report (CSR) will be prepared after the PAP analysis.

After the completion of primary analysis when all Cohort 3 patients have completed the 6-month (25 weeks) primary analysis period, interim analyses may be performed in ETP to provide additional information for regulatory purpose.

The final ETP analyses will be performed after all patients completed ETP. A final DBL will occur and a final CSR will be prepared after the ETP analyses.

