Retrospective review of available assessments prior to study entry documents clinical decline or suboptimal clinical response. It may include the following assessments:

- Respiratory function evaluation:
 - FVC (% predicted),
 - use of ventilator support.
- Motor function evaluation:
 - gross motor milestone,
 - GMFM-88 composite score,
 - Pompe-PEDI mobility,
 - QMFT,
 - GMFCS-E&R,

- other test or assessment, if any.
- Cardiac Function Evaluation:
 - Left ventricular mass (LVM) standard score (Z-score);
 - Left ventricular mass index (LVMI; g/m²);
- Other Evaluation:
 - Presence of ptosis.

The above assessments have documented (at least 2 recent and consecutive assessments prior to study entry, not less than 2 weeks apart) evidence of clinical decline or suboptimal clinical response in at least 1 of the following parameters related to Pompe disease and NOT related to intercurrent illness as assessed by the Investigator, in addition to at least 1 previous assessment prior to onset of decline:

- For patients entering Stage 1 - clinical decline in at least 1 of the following parameters: respiratory function, motor skills, and/or cardiac parameters.
- For patients entering Stage 2 - suboptimal clinical response in at least 1 of the following parameters: respiratory function, motor skills, and/or presence of ptosis.

Growth parameters at baseline

Weight (kg), height/total body length (cm), body mass index (BMI, kg/m²), head circumference (cm) and Tanner stage of sexual maturation.

Vital signs

Vital signs include systolic blood pressure, diastolic blood pressure, heart rate, respiratory rate, temperature, and oxygen saturation. The baseline values for vital signs are the last non-missing assessment prior to the first study treatment by comparing the infusion time and measurement time.

Immunogenicity status

The immunogenicity evaluation at baseline includes antibody status (positive or negative) and magnitude (titer) of the anti-drug antibodies (ADA).

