Standard 12-lead ECGs are recorded after at least 15 minutes in the supine position using an electrocardiographic device. The following will be assessed: heart rate, rhythm, interval from start of the Q wave to the end of the S wave (QRS), interval between the peaks of successive QRS complexes (RR), interval from the beginning of the P wave until the beginning of the QRS complex (PR), interval between the start of the Q wave and the end of the T wave (QT), QT interval corrected for heart rate (QTc) automatic correction evaluation (both Fredericia and Bazett corrections by the ECG device), QRS axis, left ventricular hypertrophy criteria, right ventricular hypertrophy criteria, repolarization charges, and overall cardiac impression for each patient. For Day 1 only, and prior to receiving IMP, 3 ECGs within 5 minutes will be performed with at least 1 minute between 2 replicates.

2.1.3.6 *Physical examination*

Physical examination parameters include assessments of the patient's general appearance; skin; head, eyes, ears, nose, and throat; examinations of lymph nodes, abdomen, extremities/joints, neurological and mental status; heart and respiratory auscultation; peripheral arterial pulse; and pupil, knee, Achilles, and plantar grasp reflexes. Physical examination e-CRF also asks physician to record current muscle pain and cramps specifically at each PE assessment. Tanner stage of sexual maturation will be assessed as part of the PE assessment at baseline and yearly thereafter.

2.1.3.7 *Body weight, height/total body length, and head circumference*

Body weight will be measured in kilograms and collected monthly throughout the duration of the study. More frequent weight may be obtained at the discretion of the Investigator.

Standing height or total body length will be measured at baseline and every 3 months up to Week 73 and then every 6 months and at the end of study. If possible, height will be measured in the morning of the study visit day, prior to the PFT, and by using the same stadiometer for all measurements. Standing height is preferred, but if not possible due to patient's age or physical condition, total body length is to be measured in the same position throughout the study.

BMI will be calculated as the body weight divided by the square of the body height.

Head circumference will be measured at the same time points.

2.1.3.8 *Immunogenicity*

Immunogenicity assessments will include the following:

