2.4.1 Demographics and baseline characteristics

Demographics and baseline characteristics parameters described in [Section 2.1.1](#) and physical examination parameters described in [Section 2.1.3.6](#) will be analyzed by study cohort and treatment arm among patients who received at least one dose of avalglucosidase alfa in either PAP and/or ETP, using summary statistics, based on the safety population and also in the mITT population. Denominators for the percentages will be based on the analysis population used, unless otherwise specified.

Medical history will be summarized by body system and preferred term in the safety population.

Z-scores for weight, height/total body length, BMI and head circumference will be also summarized according to the clinical growth charts of Centers for Disease Control and Prevention for applicable patients (8).

P-values on demographic and baseline characteristic data will not be calculated.

No specific description of the safety or efficacy parameters will be provided at baseline. If relevant, the baseline values will be described along with each safety or efficacy analysis.

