- Treatment-emergent algorithm-defined IARs during PAP, by PT and maximal severity, showing presented by overall n and %, as well as by start time of IAR in relation to end of infusion time (during infusion, ≤ 2 hours, >2 to 24 hours, >24 to 72 hours, >72 hours).
- Listing of AESIs during PAP.
- Listing of treatment-emergent protocol-defined IARs during PAP.

- Listing of treatment-emergent algorithm-defined IARs during PAP.

Analysis of TEAEs in ETP and overall avalglucosidase alfa treatment period

Selected PAP safety analyses will be performed for ETP and/or overall avalglucosidase alfa treatment period.

In addition, a summary table of Kaplan-Meier estimates of TEAEs by 6-month time intervals will be provided for patients who only receive avalglucosidase alfa during the overall avalglucosidase alfa treatment period (no analysis if denominator < 5).

Analysis of pre-treatment and post-treatment adverse events

- All pre-treatment AEs by primary SOC and PT.
- All AEs with onset during the post-treatment epoch for PAP or ETP by primary SOC and PT.
- All post-treatment SAEs with onset during the post-treatment epoch for PAP or ETP by primary SOC and PT.
- Listing of pre-treatment AEs.
- Listing of post-treatment AEs.

Anaphylactic/hypersensitivity reactions and potential immune-mediated reactions

A comprehensive programming search of AEs which meet the Standard MedDRA Query (SMQ) (Broad + Narrow combined and Narrow alone) criteria for hypersensitivity and anaphylactic reaction will be used to identify AEs that potentially are associated with symptoms of anaphylactic and hypersensitivity reaction. Results of this search will be provided in summary tables and in a by patient listing by group. The most recent version of MedDRA SMQ will be used at the time of analysis. A medical review of these cases will be performed.

A listing of potential immune mediated reactions will be provided. Search criteria will include but not be limited to the MedDRA PTs of glomerulonephritis, nephrotic syndrome, proteinuria, haematuria, vasculitis SMQ, serositis, myocarditis, severe cutaneous adverse reactions SMQ, skin lesion, skin necrosis, arthralgia, arthritis, myalgia, arthropathy, lymphadenopathy, serum sickness, type III immune complex mediated reaction and Influenza like illness. A medical review of these cases will be performed.

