2.4.4.6 Analyses of physical examinations

All physical examination variables will be listed by visits and summarized descriptive by study cohort and treatment group, as well as by dose levels among avalglucosidase alfa treated patients.

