Appendix B Potentially clinically significant abnormalities criteria

Measures	Adult Criteria	Pediatric Criteria
Liver function tests		
ALT	>3 x ULN	$\geq 3 \times \text{ULN}$
	>5 x ULN	$\geq 5 \times \text{ULN}$
	>10 x ULN	$\geq 10 \times \text{ULN}$
	>20 x ULN	$\geq 20 \times \text{ULN}$
AST	>3 x ULN	$\geq 3 \times \text{ULN}$
	>5 x ULN	$\geq 5 \times \text{ULN}$
	>10 x ULN	$\geq 10 \times \text{ULN}$
	>20 x ULN	$\geq 20 \times \text{ULN}$
Alkaline Phosphatase	>1.5 x ULN	$\geq 1.5 \times \text{ULN}$
Total Bilirubin	>1.5 x ULN	$\geq 1.3 \times \text{ULN}$
	>2 x ULN	
ALT and Total Bilirubin	ALT >3 x ULN and Total Bilirubin >2 x ULN	ALT $\geq 3 \times \text{ULN}$ and Total Bilirubin $\geq 2 \times \text{ULN}$
Hematology		

White Blood Cell (WBC)	<3.0 GIGA/L (non-Black), <2.0 GIGA/L (Black), ≥16.0 GIGA/L	Birth/0 to 27 days old (Neonates) <4.0 GIGA/L >25.0 GIGA/L 28 days/1 month to 23 months old (Infants) <4.0 GIGA/L >20.0 GIGA/L 24 months/2 years to <6 years old (Children) >3.0 GIGA/L >16.0 GIGA/L 6 to <12 years old (Children) <5.0 GIGA/L >17.0 GIGA/L 12 to 16/18 years old (Adolescents) <4.5 GIGA/L >13.5 GIGA/L
Lymphocytes	>4.0 GIGA/L	Birth/0 to 27 days old (Neonates) <1.2 GIGA/L >17.0 GIGA/L 28 days/1 month to 23 months old (Infants) <2.0 GIGA/L >13.5 GIGA/L 24 months/2 years to <6 years old (Children) <1.0 GIGA/L >9.5 GIGA/L 6 to <12 years old (Children) <1.0 GIGA/L >8.0 GIGA/L 12 to 16/18 years old (Adolescents) <0.6 GIGA/L >6.0 GIGA/L

Neutrophils	<1.5 GIGA/L (non-Black) <1.0 GIGA/L (Black)	Birth/0 to 27 days old (Neonates) <4.0 GIGA/L (1 day old) <1.5 GIGA/L (2 – 7 days old) <1.25 GIGA/L (>7 day – 1 month old) >1 ULN 28 days/1 month to 23 months old (Infants) <1.0 GIGA/L (1 – 3 months) <1.2 GIGA/L (3 – 24 months) >1 ULN 24 months/2 years to <6 years old (Children) <1.2 GIGA/L >1 ULN 6 to <12 years old (Children) <1.2 GIGA/L >1 ULN 12 to 16/18 years old (Adolescents) <1.2 GIGA/L >1 ULN
Monocytes	>0.7 GIGA/L	
Basophils	>0.1 GIGA/L	
Eosinophils	>0.5 GIGA/L or >ULN if ULN \geq 0.5 GIGA /L	>0.5 GIGA/L Or >ULN if ULN $>$ 0.5 GIGA/L

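### Growth belongs to the primary safety endpoint, but the SAP requires no age-standardised growth summary after baseline, which matters mainly in the uncontrolled extension

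*SAP*

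**What the plan says.** The protocol's clinical trial summary lists weight, height and head circumference within physical examination under the primary safety endpoint. SAP section 2 names "physical examinations and growth" among the safety analyses, and SAP 2.1.3 counts the three measures as safety data.

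SAP 2.1.1 lists growth parameters at baseline in physical units: "Weight (kg), height/total body length (cm), body mass index" and so on. SAP 2.4.1, on demographics and baseline characteristics, adds that "Z-scores for weight, height/total body length, BMI and head circumference will be also summarized according to the clinical growth charts" of the CDC, for applicable patients. No visit and no change from baseline is named.

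SAP 2.1.3.7 sets the schedule: weight monthly, height or length every 3 months to Week 73 and then every 6 months, and head circumference at the same time points.

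For analysis after baseline, SAP 2.4.4.6 says: "All physical examination variables will be listed by visits and summarized descriptive by study cohort and treatment group", and also by avalglucosidase alfa dose level. SAP 2.4.4 sets out the treatment groupings for extension and overall safety. Protocol 11.4.2.3 plans "Listings of abnormal findings/values from these data as well as from PE assessment inclusive of body weight and height", together with head circumference and Tanner stage. Appendix B of the SAP, "Potentially clinically significant abnormalities criteria", covers liver tests, hematology, ECG, chemistry and vital signs. It has no criterion for weight, height or head circumference.

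**The concern.** Patients are under 18 at entry and most can be expected to grow. A mean change in centimetres or kilograms is then positive whether growth is normal or slowed, so it cannot by itself show a shortfall. Measuring each child against the expected value for age and sex can.

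During the first 25 weeks the alglucosidase alfa arm of Cohort 3 offers a small concurrent comparison. After that, every patient who continues receives avalglucosidase alfa (protocol 8.1.2), so an external age reference is the only yardstick left. Raw gains also compare poorly across groups: Cohorts 1 and 2 are not randomised and Cohort 3 is stratified on gender only (protocol 8.4), so ages may differ.

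At stake is whether the planned tables could show slowed growth in a component of the primary endpoint, or whether an age-standardised summary would have to be chosen after the data are seen.

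**Working it through.** The plan gives no figure to reproduce on this point, and no test or sample size depends on it. The check has three parts.

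**1. Is an age-standardised summary required anywhere after baseline?**

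- SAP 2.4.1: supplies the CDC Z-score scale, but in the baseline section and with no later visit.
- SAP 2.4.4.6: by-visit listing and descriptive summary; no scale named. It refers to physical examination variables, which 2.1.3.6 defines, while weight, height and head circumference have their own section, 2.1.3.7.
- SAP 2.4.4: groupings for the extension and overall period; no growth scale.
- Protocol 11.4.2.3: listings of abnormal values; no standard for abnormal growth.
- SAP Appendix B: no growth criterion.

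None requires it, and none forbids it.

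**2. Where do the measurements fall?** Up to Week 145, the period this SAP covers:

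- Height and head circumference after baseline: Weeks 13, 25, 37, 49, 61, 73, 97, 121 and 145, which is 9 visits. After Week 25: 7.
- Monthly weight, Weeks 5 to 145: (145 − 5)/4 + 1 = 36. After Week 25, from Week 29: (145 − 29)/4 + 1 = 30.

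The current protocol adds nine more height visits at 24-week intervals (Weeks 169 to 361), but this SAP rests on the 27 July 2018 protocol amendment and a 3-year study.

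**3. How far can raw height and Z diverge?** Times use the target days in SAP Table 5, counted from Day 1:

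- Week 25: (169 − 1)/365.25 = 0.460 years
- Week 97: (673 − 1)/365.25 = 1.840 years
- Week 145: (1009 − 1)/365.25 = 2.760 years

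Assumed, not in the documents: expected growth v of 4 to 8 cm/year, SD of height for age of 4 to 6 cm, both constant over time, and a fractional slowing s.

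- Raw gain = (1 − s) × v × t
- Fall in Z = s × v × t / SD

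| s | Time | Raw gain (cm) | Fall in Z |
|---|---|---|---|
| 0.25 | Week 25 | 1.4 to 2.8 | 0.08 to 0.23 |
| 0.25 | Week 97 | 5.5 to 11.0 | 0.31 to 0.92 |
| 0.25 | Week 145 | 8.3 to 16.6 | 0.46 to 1.38 |
| 0.10 | Week 145 | 9.9 to 19.9 | 0.18 to 0.55 |
| 0.50 | Week 145 | 5.5 to 11.0 | 0.92 to 2.76 |

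Example, s = 0.25 at Week 145: the smallest gain is 0.75 × 4 × 2.760 = 8.28 cm. The smallest Z fall is 0.25 × 4 × 2.760/6 = 0.46 and the largest is 0.25 × 8 × 2.760/4 = 1.38.

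Age mix alone can hide the effect. A group expected to grow 8 cm/year but slowed by 25% gains 0.75 × 8 = 6 cm/year, the same as an unaffected group growing 6 cm/year. By Week 145 both have gained 6 × 2.760 = 16.6 cm. This case was built to match; it shows what is possible, not what is likely.

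**The case against.** The strongest reply is that the gap comes down to where one sentence sits. The Z-score sentence does not itself say baseline only. Section 2.4.1 ends by sending baseline safety values to the relevant safety analysis, and growth is a named safety analysis. A statistician could reasonably produce Z-scores over time under this SAP. That stands, which is why the point is that they are not required, rather than that they are excluded.

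Three stronger readings are tempting, and the documents do not support them.

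- A reader might infer that growth gets no summary at all after baseline. The protocol groups weight, height and head circumference with physical examination, and SAP section 2 commits to a growth analysis, so 2.4.4.6 most naturally covers them.
- A reader might infer that only physical units are defined. Section 2.4.1 does define a Z-score scale for these variables.
- A reader might take "Selected PAP safety analyses will be performed for ETP and/or overall avalglucosidase alfa" as all the SAP says about the extension. That sentence stands under a heading on treatment-emergent adverse events. Section 2.4.4 gives extension groupings for safety in general, and 2.4.4.6 is not confined to the first 25 weeks.

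It is also fair to say that the study is small (about 20 patients), that its safety analysis is descriptive, and that by-visit listings, adverse event reports and twice-yearly DMC review would show individual courses. Z-scores can be derived later from data already collected, and growth slowing is not among the adverse events of special interest. All of this limits the consequence. It does not supply a prespecified age-standardised summary.

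**Conclusion.** The point holds as a minor one. For a component of the primary safety endpoint, the SAP permits but does not require age-standardised summaries after baseline, and the raw summaries it would otherwise yield rise even when growth slows. The weight of the point is in the extension: 7 of 9 height visits and 30 of 36 monthly weights up to Week 145, with no concurrent control. The effect on the Week 25 analysis is small.

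The visit counts come from the documents. The Z falls do not: they depend on the assumed growth rate, SD and slowing, cover height only, and do not fit adolescents near final height. A reader might infer that the trial would miss a growth effect, or that the drug is expected to slow growth. Neither follows from the documents. No test, population or decision rule is affected.

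**What to change.** In SAP 2.4.4.6, name the 2.1.3.7 variables explicitly. Summarise the CDC Z-score and its change from baseline for weight, height or length, BMI and, for applicable patients, head circumference. Compute each Z-score from age at that assessment, using the formula already in SAP 2.1.9, and use the baseline definitions in 2.1.1. Report at each scheduled growth visit for the primary analysis period, the extension and the overall avalglucosidase alfa period, and keep raw values in the listings.

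State that interpretation is descriptive. A falling Z may reflect the disease, since scoliosis and joint contractures are recorded as Pompe history. It may also reflect measurement by length rather than standing height, although the SAP asks that "total body length is to be measured in the same position throughout the study".

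The cost is SAP wording and a few tables. The CDC reference is already cited, Z-scores are already planned, and the measurements are already collected. Sample size, error rates and patient burden do not change.

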2.4.2 Prior or concomitant medications

Prior medications and concomitant medications are defined in [Section 2.1.2](#). If a drug is started before first IMP intake but continues after the first infusion of the study drug, it is considered prior as well as concomitant.

Medications will be summarized according to the WHO-DD dictionary, considering the first digit of the Anatomical Therapeutic Chemical (ATC) classification and the first 3 digits of the ATC class (therapeutic category). All ATC codes corresponding to a medication will be summarized, and patients will be counted once in each ATC category (anatomic or therapeutic) linked to the medication. Therefore patients may be counted several times for the same medication. Prior and concomitant medications will be summarized separately using safety population.

Prior and concomitant medications will be summarized by study cohort and treatment arm in the treatment epoch for PAP among patients who receive at least one dose of alglucosidase alfa in PAP. The summary of concomitant medications will be repeated for the treatment epoch for ETP, as well as for the overall alglucosidase alfa treatment period among patients who receive at least one dose of alglucosidase alfa in ETP.

2.4.3 Extent of investigational medicinal product exposure and compliance

2.4.3.1 Extent of investigational medicinal product exposure

The extent of study drug exposure will be assessed by the duration of study drug exposure (weeks), number of infusions, amount of dose received and total duration of study drug exposure (patient \times years). The extent of study drug exposure will be summarized in the safety population.

Duration of study drug exposure is defined below:

For PAP,

- Duration of IMP exposure is defined as the first dose date in ETP (or 14 days after the last dose date in PAP if the patient is not continuing in ETP) minus (–) the first dose date in PAP, regardless of unplanned intermittent discontinuations.

For ETP,

- Duration of IMP exposure is defined as 14 days after last dose in ETP minus (–) the first dose date in ETP, regardless of unplanned intermittent discontinuations.

For the overall treatment duration,

- Duration of avalglucosidase alfa total exposure is defined as 14 days after last avalglucosidase alfa dose in study minus (–) first avalglucosidase alfa dose date in the study. This is defined for all patients other than the Cohort 3 alglucosidase alfa patients.

The duration of IMP exposure will be summarized descriptively as a continuous variable, as well as a categorical variable (e.g., <12 weeks, 12 to <24 weeks, \geq 24 weeks for PAP).

The cumulative dose information for the considered period (PAP, ETP, or the overall treatment period) will be assessed by the total number of infusions received in the considered period, as well as total amount of IMP in mL (if this information is available from the database) received in the considered period. These data will be summarized descriptively.

For Cohorts 1 and 2, and Cohort 3 avalglucosidase alfa patients, both duration of IMP exposure and cumulative dose will be summarized for PAP, ETP, as well as the overall treatment period.

For Cohort 3 alglucosidase alfa patients, both duration of IMP exposure and cumulative dose will be summarized for PAP; in addition, duration of IMP exposure will be summarized for ETP after switching to avalglucosidase alfa.

